5.3.3 Safety laboratory parameters

All safety parameters that will be determined during the trial are listed in [Table 5.3.3:1](#). Patients should be fasting for at least 8 hours prior to the blood samples taken at Visit 2 and Visit 23 or EOT. All analyses will be performed by a central laboratory. Instructions on collection, handling/ processing, and shipping of the samples will be provided in the lab manual by the central laboratory. For time points of laboratory sampling refer to the [Flow Chart](#).

Laboratory results of the patients will be available to the respective investigator and to the BI Clinical Monitor of each country (via the central laboratory website), and selected abnormal laboratory alerts will be sent automatically to the sites and to the sponsor within 24 hours.

Table 5.3.3:1 Laboratory tests

Category	Test name
Haematology	Hematocrit Hemoglobin Red Blood Cell (RBC) Count/ Erythrocytes Reticulocyte Count White Blood Cells (WBC) / Leukocytes Platelet Count/ Thrombocytes Diff. Automatic (manual if diff. automatic is abnormal) - Neutrophils - Eosinophils - Basophils - Monocytes - Lymphocytes
Coagulation	Partial Thromboplastin Time (=aPTT) Prothrombin time (Quick and INR)
Chemistry	Aspartate aminotransferase (AST/SGOT) Alanine aminotransferase (ALT/SGPT) Alkaline Phosphatase (AP) Albumin Creatine Kinase (CK) Creatine kinase myocardial b fraction (CK-MB), only if CK is elevated Gamma-Glutamyl Transferase (GGT/γ-GT) Lactic Dehydrogenase (LDH) Calcium Sodium Potassium Chloride Bicarbonate Glucose Creatinine Blood urea nitrogen (BUN) Bilirubin Total Bilirubin Direct Bilirubin Indirect Protein, Total Uric Acid Cholesterol, total Triglycerides
Chemistry (cont.)	
Pregnancy test (females only)	Human urine chorionic gonadotropin
Urinalysis (Stix)	Urine Nitrite

Category	Test name
	Urine Protein Urine Glucose Urine Ketone Urobilinogen Urine Bilirubin Urine RBC/ Erythrocytes Urine WBC/ Leukocytes Urine pH Urine creatinine
Urine-Sediment (microscopic examination), (only if urine analysis abnormal)	Urine Sediment Bacteria Urine Cast in Sediment Urine Squamous Epith Cells Urine Sediment RBC/ Erythrocytes Urine Sediment WBC/ Leucocytes
Drug screening (urine)	Amphetamines Cannabis Cocaine Methadone Opiates Phencyclidine (PCP)
Endocrine	LH, FSH, testosterone, and estrogens (e.g. estradiol) (for randomised patients only)

5.3.4 **Electrocardiogram**

The 12-lead ECGs will be performed as scheduled in the [Flow Chart](#) after 5 minutes in the supine position. The investigator or a designee will evaluate whether the ECG is normal or abnormal and whether it is clinically significant, if abnormal. The electronic version of the ECG is regarded as source data. Dated and signed printouts will be stored in the patient's medical file if there is no validated and certified e-medical record for ECG data.

ECGs may be repeated for quality reasons and the repeat used for analysis. Additional ECGs may be collected by the investigator for safety reasons. Clinically relevant abnormal findings noticed after baseline assessment will be reported as adverse events and followed up and/or treated locally until normal or stable condition.

5.3.5 **Other safety parameters**

5.3.5.1 **Assessment of suicidality**

Suicidality should be monitored closely during the study period. Suicidal thoughts and behavior will be assessed by Columbia-Suicide Severity Rating Scale (C-SSRS) ([R08-1147](#)). An electronic version (eC-SSRS) utilizing a telephone solution will be used for this trial.

The C-SSRS is a semi-structured, investigator-rated interview, developed by clinical experts in cooperation with the FDA, assessing both suicidal behavior and suicidal ideation. It does not give a global score, but provides some categorical and some severity information specifically for behavior and ideation.

The computer-automated eC-SSRS is a self-rated version of the C-SSRS using a phone, Web or tablet device. Patients who do not have suicidal behavior or ideation will answer a limited number of questions and will usually complete the assessment in about 3 minutes. Patients with significant suicidal ideation or behavior may require up to 10 minutes answering all relevant questions. This assessment should be conducted early in the visit to provide sufficient time for the report to be received at the trial site prior to patient departure. At the conclusion of each assessment, the site will receive an eC-SSRS Findings Report via email or fax. The report presents the findings for suicidal ideation, intensity of ideation, suicidal behavior, and lethality/medical damage (for actual suicide attempts only).

The C-SSRS/eC-SSRS has been widely used in large multinational clinical trials. The eC-SSRS will be administered at the Screening Visit/Visit 1 (using the 'baseline/ screening' version) with the aim to exclude patients with active moderate or severe symptomatology within a specified time prior to the screening or screening visit. The life time history of suicidal ideation and behavior will also be recorded.

After the screening visit, the assessment 'since last visit' version will be performed at each clinic or phone visit. The investigator is to review positive and negative reports for plausibility and clinical relevance. The investigator/qualified rater must perform and document an additional interview if there is doubt about the validity of the report. If there is a confirmed positive report of suicidal behavior or suicidal ideation type 4 or 5 after start of trial, the investigator is to immediately interview the patient, and/or is to consult a psychiatrist. If the positive report is confirmed, appropriate actions for the patient's safety have to be initiated.

All C-SSRS reports of suicidal ideation type 4 or 5 and all reports of suicidal behavior must be reported as separate SAEs by the investigator.

For 'Self-injurious behavior, without suicidal intent', standard AE / SAE reporting rules are to be applied.

For each negative report (suicidal ideation type 1, 2 or 3) after start of the trial, the investigator is to decide based on clinical judgment whether it represents an Adverse Event (AE) as defined in the protocol, and if it is considered an AE then it must be reported accordingly. See Section 5.3.6.

The patient should be withdrawn from treatment if the patient exhibits suicidality and meets the withdrawal criteria mentioned in [Section 3.3.4.1](#).

5.3.6 Assessment of adverse events

5.3.6.1 Definitions of AEs

Adverse event

An adverse event (AE) is defined as any untoward medical occurrence in a patient or clinical investigation patient administered a medicinal product and which does not necessarily have to have a causal relationship with this treatment.

An AE can therefore be any unfavourable and unintended sign (including an abnormal laboratory finding), symptom, or disease temporally associated with the use of a medicinal product, whether or not considered related to the medicinal product.

Serious adverse event

A serious adverse event (SAE) is defined as any AE, which fulfils at least one of the following criteria:

- results in death,
- is life-threatening, this refers to an event in which the patient was at risk of death at the time of the event; it does not refer to an event that hypothetically might have caused death if more severe.
- requires inpatient hospitalisation or prolongation of existing hospitalisation,
- results in persistent or significant disability or incapacity, or
- is a congenital anomaly / birth defect,
- is deemed serious for any other reason if it is an important medical event when based on appropriate medical judgment which may jeopardise the patient and may require medical or surgical intervention to prevent one of the other outcomes listed in the above definitions. Examples of such events are intensive treatment in an emergency room or at home for allergic bronchospasm, blood dyscrasias or convulsions that do not result in hospitalisation or development of dependency or abuse.

All C-SSRS reports of suicidal ideation type 4 or 5 and all reports of suicidal behavior after the baseline visit must be reported as separate SAEs by the investigator. For ‘Self-injurious behavior, without suicidal intent’, standard AE / SAE reporting rules are to be applied (see [Section 5.3.5.1](#) for details).

AEs considered “Always Serious”

In accordance with the European Medicines Agency initiative on Important Medical Events, Boehringer Ingelheim has set up a list of further AEs, which by their nature, can always be considered to be “serious” even though they may not have met the criteria of an SAE as given above.

The latest list of “Always Serious AEs” can be found in the Electronic Data Capture (EDC) system. These events should always be reported as SAEs as described above.

Note: Cancers of new histology and exacerbations of existing cancer must be reported as a serious event regardless of the duration between discontinuation of the drug and the occurrence of the cancer.

Adverse events of special interest (AESIs)

The term AESI relates to any specific AE that has been identified at the project level as being of particular concern for prospective safety monitoring and safety assessment within this trial, e.g. the potential for AEs based on knowledge from other compounds in the same class. AESI need to be reported to the sponsor’s Pharmacovigilance Department within the same timeframe that applies to SAE, please see above.

The following are considered as AESIs:

Hepatic injury

A hepatic injury is defined by the following alterations of hepatic laboratory parameters:

- an elevation of AST and/or ALT ≥ 3 fold ULN combined with an elevation of total bilirubin ≥ 2 fold ULN measured in the same blood draw sample, and/or
- aminotransferase (ALT, and/or AST) elevations ≥ 10 fold ULN

These lab findings constitute a hepatic injury alert and the patients showing these lab abnormalities need to be followed up according to the “DILI checklist”, which can be found in EDC. In case of clinical symptoms of hepatic injury (icterus, unexplained encephalopathy, unexplained coagulopathy, right upper quadrant abdominal pain, etc.) without lab results (ALT, AST, total bilirubin) available, the Investigator should make sure these parameters are analysed, if necessary in an unscheduled blood test. Should the results meet the criteria of hepatic injury alert, the procedures described in the DILI checklist should be followed.

No other AESIs have been defined for this trial.

Intensity of AEs

The intensity of the AE should be judged based on the following:

Mild: Awareness of sign(s) or symptom(s) that is/are easily tolerated

Moderate: Enough discomfort to cause interference with usual activity

Severe: Incapacitating or causing inability to work or to perform usual activities

Causal relationship of AEs

Medical judgment should be used to determine whether there is a reasonable possibility of a causal relationship between the adverse event and the given study treatment, considering all relevant factors, including pattern of reaction, temporal relationship, de-challenge or re-challenge, confounding factors such as concomitant medication, concomitant diseases and relevant history.

Arguments that may suggest that there is a reasonable possibility of a causal relationship could be:

- The event is consistent with the known pharmacology of the drug
- The event is known to be caused by or attributed to the drug class.
- A plausible time to onset of the event relative to the time of drug exposure.
- Evidence that the event is reproducible when the drug is re-introduced
- No medically sound alternative aetiologies that could explain the event (e.g. pre-existing or concomitant diseases, or co-medications).
- The event is typically drug-related and infrequent in the general population not exposed to drugs (e.g. Stevens-Johnson syndrome).
- An indication of dose-response (i.e. greater effect size if the dose is increased, smaller effect size if dose is diminished).

Arguments that may suggest that there is no reasonable possibility of a causal relationship could be:

- No plausible time to onset of the event relative to the time of drug exposure is evident (e.g. pre-treatment cases, diagnosis of cancer or chronic disease within days / weeks of drug administration; an allergic reaction weeks after discontinuation of the drug concerned)
- Continuation of the event despite the withdrawal of the medication, taking into account the pharmacological properties of the compound (e.g. after 5 half-lives). Of note, this criterion may not be applicable to events whose time course is prolonged despite removing the original trigger.
- Additional arguments amongst those stated before, like alternative explanation (e.g. situations where other drugs or underlying diseases appear to provide a more likely explanation for the observed event than the drug concerned).
- Disappearance of the event even though the study drug treatment continues or remains unchanged.

5.3.6.2 Adverse event collection and reporting

AE Collection

Patients will be required to report spontaneously any AEs as well as the time of onset, duration and intensity of these events.

If patients report a change in perception or any vision-related AE, site staff must record the patient's verbatim description in the source documents to be reported in the eCRF (and SAE form if applicable). A local ophthalmology assessment will be required if any visual AE is rated as severe by the patient or at the discretion of the Principal Investigator. The ophthalmologist will act as a consultant to the Investigator and may offer advice on the proper management and treatment for the reaction.

The potential for study drug abuse-related adverse events will be closely monitored and narratives provided in the CTR. Narratives will include standard AE data collection, including time of onset, duration, severity and outcome.

The Investigator shall maintain and keep detailed records of all AEs in their patient files. The following must be collected and documented on the appropriate CRF(s) by the Investigator:

- From signing the informed consent/assent onwards through the Residual Effect Period (REP), until individual patient's end of trial:
 - all AEs (serious and non-serious) and all AESIs.
- After the individual patient's end of trial:
the Investigator does not need to actively monitor the patient for AEs but should only report relevant SAEs and relevant AESIs of which the Investigator may become aware of by any means of communication, e.g. phone call. Those AEs should be reported on the BI SAE form, but not on the CRF.

The rules for Adverse Event Reporting exemptions still apply, please see [Section 5.3.6.3](#).

[figure not shown]

Figure 5.3.6.2: 1 AE Collection

Patients who discontinue trial medication prematurely and agree to be contacted further, should be followed up as described in [Section 3.3.4.1](#), withdrawal from trial treatment. From then on until the individual patient's end of the trial the investigator must report:

- All AEs/SAEs/AESIs collected by the investigator as instructed in [Section 3.3.4.1](#) for patients who choose Options 1 and 2.
- All AEs/SAEs/AESIs the investigator becomes aware of for patients who choose Options 3 and 4

After the individual patient's end of the trial the Investigator does not need to actively monitor the patient for AEs but should only report relevant SAEs and relevant AESIs of which the Investigator may become aware of by any means of communication, e.g. phone call. Those AEs should be reported on the BI SAE form, but not on the CRF.

The rules for Adverse Event Reporting exemptions still apply, please see [Section 5.3.6.3.](#)

The REP is defined as 7 days after the last dose of trial medication is taken. All AEs which occurred through the treatment phase and throughout the REP will be considered as on treatment, please see [Section 7.3.4.](#) Events which occurred after the REP will be considered as post treatment events.

AE reporting to sponsor and timelines

The Investigator must report SAEs, AESIs, and non-serious AEs which are relevant for the reported SAE or AESI, on the BI SAE form via fax immediately (within 24 hours) to the sponsor's unique entry point (country specific contact details will be provided in the ISF). The same timeline applies if follow-up information becomes available. In specific occasions the Investigator could inform the sponsor upfront via telephone. This does not replace the requirement to complete and fax the BI SAE form.

With receipt of any further information to these events, a follow-up SAE form has to be provided. For follow-up information the same rules and timeline apply as for initial information.

Information required

For each AE, the Investigator should provide the information requested on the appropriate CRF pages and the BI SAE form. The Investigator should determine the causal relationship to the trial medication.

The following should also be recorded as an (S)AE in the CRF and SAE form (if applicable):

- Worsening of the underlying disease or of other pre-existing conditions
- Changes in vital signs, ECG, physical examination and laboratory test results, if they are judged clinically relevant by the Investigator.

If such abnormalities already pre-exist prior to trial inclusion they will be considered as baseline conditions.

All (S)AEs, including those persisting after an individual patient's end of trial must be followed up until they have resolved, have been sufficiently characterised, or no further information can be obtained.

Pregnancy

In rare cases pregnancy may occur in a clinical trial. Once a patient has been enrolled into this clinical trial and has taken trial medication, the Investigator must report immediately (within 24 hours) a potential drug exposure during pregnancy (DEDP) to the sponsor's unique entry point (country-specific contact details will be provided in the ISF). The Pregnancy Monitoring Form for Clinical Trials (Part A) should be used.

The outcome of the pregnancy associated with the drug exposure during pregnancy must be followed up and reported to the sponsor's unique entry point on the Pregnancy Monitoring Form for Clinical Trials (Part B). The ISF will contain the Pregnancy Monitoring Form for Clinical Trials (Part A and B).

As pregnancy itself is not to be reported as an AE, in the absence of an accompanying SAE and/or AESI, only the Pregnancy Monitoring Form for Clinical Trials and not the SAE form is to be completed. If there is an SAE and/or AESI associated with the pregnancy an SAE form must be completed in addition.

5.3.6.3 Exemptions to SAE reporting

Psychosis is considered an Outcome Event and is exempted from reporting as an SAE. See [Section 5.1.2](#) for the definition of psychosis. However, when there is evidence suggesting a causal relationship between study drug and an episode of psychosis, the event must immediately be reported as an SAE on the SAE form and on the appropriate eCRF.

Psychosis events determined not related to study drug should be recorded on the appropriate pages of the eCRF as part of efficacy data collection. These outcome events will be collected, adjudicated by the Central Rating Committee, and monitored by the DMC.

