4.2 OTHER TREATMENTS, EMERGENCY PROCEDURES, RESTRICTIONS

4.2.1 Other treatments and emergency procedures

If a patient is enrolled who is taking an antipsychotic medication that will continue during the treatment period, it is extremely important they continue to take the current antipsychotic medication at the same dose as when the patient was randomized. The dose of an antipsychotic medication can be decreased or discontinued entirely. A patient's dose of antipsychotic medication should be increased only in circumstances of significant worsening of psychosis symptoms that the investigator feels qualifies for a first episode of psychosis. Patients experiencing a first episode of psychosis should continue taking study drug at the discretion of the investigator.

When a patient begins a new prescription or increases their dose of an ongoing antipsychotic medication, this is an outcome event. The available information (e.g., SOPS interview video, medical records from prescribing physician) will be subsequently reviewed by the Central Rating Committee.

Antipsychotic medications will not be provided as part of the clinical trial supplies.

Any change in dose of concomitant antipsychotic medications should be recorded in the source documentation and on the appropriate pages of the eCRF. Prior and concomitant psychotherapy information should also be recorded in the eCRFs.

All patients (i.e., including those on BI 409306 and those on placebo) will receive Brief Supportive Psychoeducation at timepoints described in the [Flow Chart](#). The supportive psychoeducation sessions will be administered by trained site staff and will educate patients and family members about the symptoms of attenuated psychosis syndrome as well as the clinical trial program, risk and protective factors, the impact of stress and the importance of medication adherence. Through these sessions, the patient's and family's needs are evaluated, a symptom reduction plan is developed and referrals for community services may be provided. Refer to Psychoeducation Manual and Materials in ISF.

Any additional treatment that is considered necessary for the patient's welfare may be given at the discretion of the Investigator.

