5.1.2 Secondary Endpoints

- Time to first episode of psychosis within a 52 week timeframe as adjudicated by the Central Rating Committee. First episode of psychosis defined as one or more SOPS P1-P5 rated a 6 AND either a symptom is seriously disorganized or dangerous OR one of the symptoms above occurred at least one hour per day at an average frequency of four days/week over the past month. OR a new prescription or increase in dose of an ongoing antipsychotic medication. Time of onset of first episode psychosis is defined using the rater's best estimate as determined in the SOPS interview or when

the patient began taking a new prescription or increased the dose of antipsychotic medication.

- Change from baseline in everyday functional capacity as measured by Schizophrenia Cognition Rating Scale (SCoRS) total score after 24 and 52 weeks of treatment.
- Change from baseline in the BAC App composite T score after 52 weeks of treatment.
- Change from baseline in Positive and Negative Syndrome Scale (PANSS) positive items score, negative items score, and total score after 52 weeks of treatment.

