8.4 EXPEDITED REPORTING OF ADVERSE EVENTS

BI is responsible to fulfil their legal regulatory reporting obligation and in accordance with regulatory requirements defined in this CTP. Psychosis events are considered outcome events and are not to be reported as SAEs, unless if considered related to trial medication. See [Section 5.3.6.3](#).

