7.8.1 Adverse events

Unless otherwise specified, the analyses of adverse events will be descriptive in nature. All analyses of AEs will be based on the number of subjects with AEs and NOT on the number of AEs.

The analysis of adverse events will be based on the concept of treatment emergent adverse events. That means all adverse events with an onset between start of treatment and end of the on-treatment period, which is 7 days after the last dose of trial medication, will be assigned to the treatment period for evaluation. All adverse events occurring before first drug intake will be assigned to 'screening' and all adverse events occurring after the residual effect period will be assigned to 'post-treatment' (for listings only).

According to ICH E3 (5), AEs classified as 'other significant' need to be reported and will include those non-serious and non-significant adverse events with:

- (i) 'action taken = discontinuation' or 'action taken = reduced', or
- (ii) marked haematological and other lab abnormalities or lead to significant concomitant therapy as identified by the Clinical Monitor/Investigator at a Medical Quality Review Meeting.

An overall summary of adverse events will be presented. The frequency of subjects with adverse events, and will be summarized by treatment, primary system organ class and

preferred term. Separate tables will be provided for subjects with other significant adverse events according to ICH E3 (5), for subjects with adverse events of special interest (only if defined) and for subjects with serious adverse events.

The system organ classes and preferred terms (within system organ class) will be sorted by frequency.

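### Psychosis enters the SAE table by attribution rather than seriousness, and later episodes judged unrelated have no planned by-arm tabulation in the readable SAP

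*Protocol*

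**What the plan says.** **Exemption.** Protocol 5.3.6.3 states: "Psychosis is considered an Outcome Event and is exempted from reporting as an SAE". The exception applies "when there is evidence suggesting a causal relationship between study drug and an episode of psychosis"; such an event is reported as an SAE at once. Section 8.4 repeats the rule: "Psychosis events are considered outcome events and are not to be reported as SAEs, unless if considered related to trial medication". Section 5.3.6.2 gives the causality judgement to the investigator. Of the remaining events, 5.3.6.3 says: "Psychosis events determined not related to study drug should be recorded on the appropriate pages of the eCRF as part of efficacy data collection". They are adjudicated by the Central Rating Committee and monitored by the DMC.

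**Scope.** Section 5.3.6.3 takes its definition of psychosis from 5.1.2, which defines a first episode and includes the limb "OR a new prescription or increase in dose of an ongoing antipsychotic medication". Flow Chart footnote 20 makes psychosis events after randomisation Outcome Events, without restriction to the first. Section 5.3.6.2 lists among the items to be recorded as an (S)AE: "Worsening of the underlying disease or of other pre-existing conditions".

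**After a first episode.** Section 2.3 keeps patients who convert in follow-up. Section 4.2.1 says: "Patients experiencing a first episode of psychosis should continue taking study drug at the discretion of the investigator".

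**Analysis.** SAP 7.8.1 plans an overall AE summary and separate tables for other significant AEs, for AEs of special interest "and for subjects with serious adverse events". It counts subjects, not events. SAP 7.5.2 compares time to first episode of psychosis between arms with a Cox model.

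**The concern.** For any other event, SAE status follows from what happened to the patient: hospital admission, threat to life, disability and so on. For psychosis it follows from whether the investigator thinks the drug was responsible. Two equally severe episodes can be filed differently, and only one of them reaches the SAE table. A reader comparing the arms on serious psychiatric events would not know that the psychosis rows are a subset selected by attribution.

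The efficacy analysis restores part of what is lost, because it counts first episodes regardless of causality. It does not say which were serious, and it stops at the first. Patients observed after conversion, some of them still on study drug, can have further episodes. If these are judged unrelated, no planned comparison in the readable SAP would show them. At stake is whether the report can describe serious psychosis by arm completely.

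**Working it through.** The documents give no figure for the share of psychosis that is serious, judged related or recurrent. The check is therefore made by following each kind of episode through the planned outputs. The sample-size and power figures in Protocol 7.7 concern remission and are not inputs here.

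**Step 1: where each episode goes under the exemption.**

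| Episode | Judged related | Judged unrelated |
|---|---|---|
| First | SAE report and SAE table (if treatment-emergent); time to first episode | Efficacy eCRF pages; time to first episode |
| Later | SAE report and SAE table (if treatment-emergent) | Efficacy eCRF pages; no by-arm tabulation in the readable SAP |

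Seriousness does not decide any cell. A related episode is an SAE without reference to the seriousness criteria of 5.3.6.1, and an unrelated one is exempt even if it meets them.

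**Step 2: what the SAE table then estimates.** SAP 7.8.1 counts subjects. In each arm:

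subjects with a psychosis SAE = subjects with psychosis × share of them with at least one treatment-emergent episode judged related.

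If that share is the same value r in both arms, the difference shown is r times the difference in subjects with psychosis. If it differs between arms, the ratio shown is the true ratio multiplied by the ratio of the shares. The documents give neither r nor any evidence of a difference, so no numerical result follows.

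**Step 3: what the first-episode analysis restores.** Protocol 5.1.2 and SAP 7.5.2 set no causality condition, so first episodes are compared without the filter. The endpoint definition contains no seriousness element. There is one further limit, which depends on reading. SAP 7.5.2 refers to the method of the primary analysis, and Protocol 7.3.1 runs that analysis on the on-treatment period, which ends 7 days after drug discontinuation. If the period carries over, first episodes after that point also fall outside the main comparison. The full follow-up sensitivity analysis in SAP 7.4.1 is stated for the primary endpoint only.

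**Step 4: whether later unrelated episodes are exempt at all.**

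- 5.3.6.3 points to a definition of the first episode only. Read strictly, a later episode is not covered.
- Flow Chart footnote 20 covers all psychosis after randomisation. Read with 5.3.6.3, a later episode is covered.
- 5.3.6.2 sends worsening of the underlying disease to (S)AE recording. It cross-refers to the exemption twice, each time after text about the period following the patient's end of trial, and not beside the worsening line.

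Sites could apply any of these readings, and the same later episode could be an SAE at one site and efficacy data at another.

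**The case against.** The strongest case on the other side is that this is a deliberate and common design. Psychosis is an efficacy outcome, it is centrally adjudicated, and the DMC watches it during the trial. First episodes are compared by arm without a causality filter, PANSS scores are compared by arm, and suicidal behaviour and ideation of type 4 or 5 are SAEs whatever their cause (Protocol 5.3.5.1). All of this stands. It limits the point to psychosis in the SAE table and to later unrelated episodes. DMC monitoring does not put a table in the report.

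It is also fair that parts of the SAP are redacted and that the eCRF is not available. An outcome-event table or seriousness fields may already exist. The point is therefore confined to the readable SAP, and the eCRF request is conditional.

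Four stronger readings are tempting and are not supported:

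- **That no episode after the first reaches the SAE tables.** The exception in 5.3.6.3 refers to an episode, not to the first, so a related later episode is an SAE.
- **That the filter biases the comparison against or in favour of the drug.** Causality is judged under blinding (4.1.5.1). Visual effects soon after dosing could hint at allocation, but nothing shows that attribution would differ by arm.
- **That 5.3.6.2 contradicts 5.3.6.3.** It cross-refers to the exemption, so the texts are unreconciled rather than opposed.
- **That any serious crisis treated with an antipsychotic becomes exempt.** Section 4.2.1 makes the prescription an outcome event, but nothing says that a separate event meeting the SAE criteria stops being reportable.

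**Conclusion.** The point holds in a limited form. Under the plan as written, the SAE table counts psychosis by attribution. The first-episode analysis is free of that filter but silent on seriousness. Later episodes judged unrelated have no planned by-arm tabulation in the readable SAP. The scope of the exemption for those later episodes is unsettled between Flow Chart footnote 20, 5.3.6.2 and 5.3.6.3.

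The size cannot be stated. It depends on how many episodes are serious, how many are judged related and how many patients have more than one, and the documents give none of these. SAP section 4 adds that the trial is much smaller than intended, so planned arm sizes would not be a sound basis for an illustration.

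A reader might also infer that the trial can say nothing about the finding in Protocol 1.2 that all eight psychiatric SAEs in an earlier schizophrenia trial were on placebo. That goes too far. The protocol does not say those events were psychosis, and other psychiatric SAEs remain reportable here.

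No endpoint, alpha, power or sample-size figure is affected. This is a cheap improvement to safety reporting and not a flaw in the efficacy analysis. It assumes that the redacted SAP sections hold no equivalent table.

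**What to change.** Keep the expedited-reporting exemption and make three changes.

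1. On the outcome-event eCRF page, record the SAE seriousness criteria for every psychosis outcome event, whatever its causality, if they are not already captured. Where the page can no longer be changed, take them from the records gathered for adjudication, so far as these allow.
2. In SAP 7.8.1 add one descriptive by-arm table of all psychosis outcome events regardless of causality, giving subjects and episodes. Split it by first and later, serious and non-serious, on-treatment and post-treatment, and SOPS-based versus antipsychotic change only. State that the SAE table is to be read beside it.
3. Reconcile Flow Chart footnote 20, the worsening line in 5.3.6.2 and the exemption in 5.3.6.3, so that the handling of later episodes is the same at every site.

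The cost is slightly more data entry (or record retrieval) and one extra table.
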